## **Statistical Analysis Plan**

### **Insulin Resistance Intervention after Stroke Trial**

#### **Background**

Among 400,000 Americans who survive an ischemic stroke or TIA each year, a major source of morbidity and mortality is recurrent stroke and myocardial infarction. Within 5 years of the initial event, 18% of patients will have a recurrent stroke, 9% will have a myocardial infarction, and 6% will die from one of these two conditions. Prevention of further vascular events, therefore, is of major importance in reducing the morbidity and mortality of stroke. Current strategies for preventing vascular events after stroke include antiplatelet therapy, hypertension control, anticoagulation, lipid management, and carotid endarterectomy. Despite these effective strategies, many suitably treated stroke patients still experience recurrent vascular events. New therapeutic approaches are urgently needed.

The Insulin Resistance Intervention after Stroke (IRIS) trial proposes an innovative therapy based on 20 years of accumulating evidence linking insulin resistance to increased risk for stroke and other vascular diseases. The aim of the IRIS trial is to determine if pioglitazone, an agent that reduces insulin resistance and has other potent vasoprotective effects, is effective in lowering the risk for stroke or myocardial infarction among non-diabetic men and women 40 years of age and older with a recent ischemic stroke or TIA and insulin resistance. The IRIS trial will determine the effectiveness of a new strategy, the treatment of insulin resistance in non-diabetic subjects, for preventing recurrent stroke and myocardial infarction after ischemic stroke or TIA. Since insulin resistance is estimated to affect 50% of stroke patients, this innovative treatment has the potential to benefit a large number of patients. The study will also yield important data on the effectiveness of pioglitazone in preventing progression to overt diabetes, and in reducing the risks for all-cause mortality and cognitive decline.

#### **Primary Objective**

1. To determine if pioglitazone, compared to placebo, will reduce the overall risk for fatal or non-fatal stroke or fatal or non-fatal MI among non-diabetic men and women 40 years or older with insulin resistance and a recent ischemic stroke or TIA.

Among non-diabetics with insulin resistance, we hypothesize that pioglitazone will reduce the occurrence of any primary endpoint (fatal or non-fatal stroke or MI) within four years from 27% to 22%.

#### **Secondary Objectives**

1. To determine if pioglitazone, compared to placebo, will reduce the risk for recurrent stroke.

We hypothesize that pioglitazone will reduce the occurrence of recurrent fatal or non-fatal stroke as a discrete outcome.

2. To determine if pioglitazone, compared to placebo, will reduce the risk for acute coronary syndromes (ACS) (acute MI or unstable angina).  
Unstable angina is an important clinical event because it identifies individuals at high risk for MI who need urgent diagnostic and therapeutic intervention. We hypothesize that pioglitazone will reduce the overall occurrence of acute coronary syndromes.
3. To determine if pioglitazone, compared to placebo, will reduce the risk for all-cause mortality.  
We hypothesize that pioglitazone will reduce all-cause mortality because of its vasoprotective effects.
4. To determine if pioglitazone, compared to placebo, will reduce the risk for recurrent stroke, MI, or serious congestive heart failure (CHF).  
We hypothesize that pioglitazone will reduce the occurrence of recurrent fatal or non-fatal stroke, MI or CHF.
5. To determine if pioglitazone, compared to placebo, is effective in preventing progression to overt diabetes.  
Insulin resistance is the principal risk factor for type II diabetes. We hypothesize that pioglitazone, by sensitizing cells to insulin's action, will prevent progression to diabetes.
6. To determine if pioglitazone, compared to placebo, will reduce the risk for cognitive decline.  
We hypothesize that pioglitazone will reduce the risk for cognitive decline by reducing the incidence of clinically apparent and unapparent stroke.

### Study Design

The Insulin Resistance Intervention after Stroke Trial (IRIS) is a double-blind, placebo-controlled, multi-center clinical trial in which approximately 4000 non-diabetic patients  $\geq 40$  years of age with insulin resistance and a recent non-disabling ischemic stroke or TIA are randomly assigned to pioglitazone, a thiazolidinedione (TZD), or placebo. Randomization is stratified by participating site using a random permuted block design of varying block size (4, 6, 8) and treatment allocation ratio of 1:1 between placebo and active drug. Maximum follow-up will be 5 years (plus 21 days allowed after the 5 year anniversary to complete the exit interview) and the average follow-up duration will be approximately four years. Participants who experience a stroke or MI during follow-up will be maintained on their randomized study drug and will continue to be followed for the occurrence of other primary and secondary outcomes until they are withdrawn at trial termination or are censored due to death.

To rigorously evaluate the effect of treatment on each defined secondary outcome, the strategy of retaining participants on treatment after a primary endpoint is considered as a requirement. A participant who experiences an MI at day 60 after randomization and a subsequent stroke at day 300 will be analyzed as an outcome for the primary analysis at day 60 (time to first stroke or MI). However, for the analysis of stroke alone, a participant will be counted as event free until day 300 (time to first stroke). This design allows for the detection of an effect of treatment

on stroke regardless of the treatment effect on the occurrence of MI. Similar contingencies pertain for the other secondary outcomes.

The occurrence of initial vascular events may affect a participant's ability and willingness to continue on his or her assigned study drug. Although all analyses will be conducted according to the intention-to-treat principle, an early effect of treatment on one type of outcome (e.g., stroke) may systematically alter compliance by treatment group, thus affecting the ability to detect an effect of treatment on later events. Because of this concern, every effort will be made to maintain each participant on his or her assigned treatment, both before and following any vascular event they may experience.

### Interim Monitoring Plan

Interim monitoring is performed by the Statistical Center and focuses on recruitment (overall and by site), prevalence of insulin resistance, baseline comparability of treatment groups, protocol adherence, completeness of data retrieval, accrual of primary endpoint events (i.e., information accrual), safety and treatment efficacy. Recruitment, prevalence of insulin resistance, and completeness of data retrieval are also monitored by the Coordinating Center for purposes of daily trial operations and quality assurance. Independent and definitive monitoring by the Statistical Center; however, serves as a check on the Coordinating Center and provides the basis for reporting to the DSMB.

- *Monitoring for Recruitment and Prevalence of Insulin Resistance*

The Coordinating Center will monitor all steps in recruitment to assure early recognition of inadequate performance and identify reasons for inadequate performance in each recruitment site and in the trial overall. To assist in this process the Statistical Center will provide the Coordinating Center with data monitoring reports. These reports will include number of screening log entries, reasons for ineligibility on log, number of screener forms completed, reasons for ineligibility at screening, number of informed consent documents signed, number of screening HOMA tests obtained, the prevalence of insulin resistance (i.e., HOMA >3.0) among screened individuals, and randomizations. Each recruitment site's randomization performance is gauged in relation to its specific recruitment goal. The same reports are available at each DSMB meeting. Among the advantages of continuous monitoring of recruitment, the resulting data gives the DSMB an early and regular opportunity to compare the trial assumptions with the observed data to make early judgments about the merits of continuing the research. For example, within one year of initiation of funding, it is anticipated that 1506 will be screened with HOMA testing. The DSMB may consider stopping the trial or modifying the design if the observed prevalence of insulin resistance (HOMA >3.0) is substantially less than the assumed 45% and results in lower than expected rates of accrual and information (events).

- Baseline Comparability

The adequacy of randomization is assessed by comparing the distribution of baseline characteristics among the treatment groups: demographics, physical and medical history measures, symptoms and complaints, prescription and non-prescription medications. Continuous variables are examined for skewness, outliers, or other departures from a normal distribution graphically and by summary statistics. F tests for equality of variances are used to determine the appropriate statistical test for continuous measures. Categorical variables are examined by calculating frequency distributions.

- Protocol adherence

Protocol adherence is monitored monthly by the Operations Committee to assure early identification of poor performance at individual sites and in the trial overall. Periodic reports are provided to the DSMB and whenever requested. Specific parameters to be monitored include:

- Randomization of ineligible participants
- Treatment allocation errors (participant put on wrong treatment)
- Failure to obtain required blood tests on time
- Failure to complete required follow-up interviews on time
- Loss and withdrawal rates
- Treatment adherence (pill counts, cessation of use)
- Failure to complete endpoint adjudication on time (within 30 days)
- Use of TZDs outside of trial protocol
- Continued use of trial medication despite contra-indication (e.g., hemoglobin <8.5 g/dl, ALT >2.5x upper limit of normal)

- Monitoring for Efficacy

Three interim “looks” at the primary endpoint data for treatment efficacy are planned. The proposed stopping boundaries for the interim analyses are based on the work of Lan and DeMets and of Wang and Tsiatis and are calculated using East Version 4. Since it is unlikely that there will be an adequate number of events during the first year to evaluate efficacy, interim “looks” are proposed after 227 events (one-fourth of total events), 454 events and 681 events are observed in the trial cohort, with the final analysis at 908 events, the total number of events selected for the trial. The stopping boundaries are designed to be flexible; therefore, the actual timing of the analyses will be based on Data and Safety Monitoring Board request. The Data and Safety Monitoring Board will review all interim analyses. If the interim analyses indicate a significant treatment effect or a very low conditional probability of detecting the estimated treatment effect (see Figure 1), the DSMB may choose to stop the trial prematurely.

- Monitoring for Futility

A futility analysis for the primary endpoint is planned during the 2nd and 3rd interim analyses (see Figure 1), which will occur after approximately 454 events of stroke or MI events have been observed and after 681 events. If either of these analyses shows that the nominal critical point (Z-score) for the primary endpoint crosses the internal boundary for futility, it would indicate that the observed effect size is much smaller than anticipated and that the trial has very low conditional power to detect the estimated treatment effect for the primary outcome. In addition to these futility analyses, the observed primary outcome event rate and rate of information accrual (number of events) is monitored from the initiation of the trial and compared with the expected rates. Based on these rates an estimated time for study completion (i.e. time to reach 908 events) and the estimated number of events that will be reached by the scheduled end of the trial is presented to the DSMB. When considering the futility analyses and rate of information accrual, the DSMB may also consider other internal evidence of futility (i.e., secondary outcomes) and has the option of recommending early termination of the trial or continuing with a possible adjustment to sample size.

[figure not shown]

Figure 1. Proposed Stopping Boundaries for Three Interim Analyses. Interim analyses will be performed after 227, 454 and 681 endpoints are observed in the trial cohort. If the nominal critical point falls in the outer shaded area (indicating a significant treatment effect) or the inner shaded area (indicating a very low conditional probability of detecting the estimated treatment effect), the DSMB may choose to stop the trial prematurely.

- *Analysis of Adverse Events*

The incidence of serious adverse events, as defined by the International Conference on Harmonization and FDA guidelines, and the incidence of non-serious adverse events including headache, muscle aches, sinusitis, pharyngitis, teeth problems, edema, weight gain, shortness of breath, elevated ALT,) are calculated and compared among the treatment groups using statistics appropriate for discrete or count data. To track changes in weight over time, mean changes and the proportion of participants with an increase of 5% and 10% in body weight from baseline will be compared between the two treatment groups at each time point. In addition, the incidence of all cancers (and bladder cancer specifically), liver failure, serious congestive heart failure, serious macular edema, and bone fracture are analyzed by treatment group. Initially, due to the presence of small counts of serious and non-serious adverse events before data collection completion, the Fisher's exact test are used for comparing proportions with no (adverse) events with proportions with one or more (adverse) events among treatment groups. Finally, the effect of treatment on all-cause mortality as a time to event analysis is monitored as an additional safety endpoint.

### Study Outcomes

The primary outcome measure is time to first fatal or non-fatal stroke or fatal or non-fatal MI. There are six secondary outcomes for this study: time to first stroke; time to first episode of Acute Coronary Syndrome (MI or unstable angina); all-cause mortality; the composite of time to first stroke, MI or serious CHF; time to first developing diabetes; and the modified mini mental state exam longitudinal scores. The date of randomization will be used as the time origin for a participant's study period. Time to censoring will be defined as time in days from date of randomization until the date of last contact. Contact will be defined as direct contact with the patient or a pre-defined surrogate. Database review will not be considered sufficient contact to determine event free time except in certain circumstances for all-cause mortality only (see below). Events detected through database searches will be counted if adjudicated as an event.

Participants are to be exited during an exit interview at the end of five years of study participation or at the last scheduled contact that falls between March 9, 2015 and July 7, 2015, whichever comes first.

Maximum follow-up will be 5 years plus a 21 day allowance for late completion of the exit interview (1847 days total).

Outcome and safety events will not be counted in the analysis if they occur after the date of completion of the exit interview. In addition, outcome and safety events will not be counted if they occur more than 21 days after the scheduled date of an exit interview that was not completed or completed late.

The IRIS trial will have endpoint review committees for stroke, acute coronary syndromes, and diabetes. Each committee will be comprised of a chair and three or more physicians who are specialists in the committee's content area. Reviewers will receive training in the application of specific criteria for declaring and classifying endpoints in their specialty. Reviewers will be blinded to treatment allocation. For suspected stroke endpoints, neurologists on the endpoint committee will decide whether a stroke has occurred and determine the stroke subtype. For suspected cardiac endpoints, cardiologists on the committee will decide if an acute coronary event has occurred and whether it was an MI or episode of unstable angina. The diagnosis of fatal MI includes participants who die after presentation with acute MI and cases of well documented sudden death. For suspected incident cases of diabetes, endocrinologists on the committee will decide if metabolic data fulfill the case definition.

The IRIS investigators will apply to the National Death Index (NDI) for information on patients who have been lost to follow-up, if approved by governing investigational review boards. At least two searches will be performed, one shortly after completion of enrollment and one approximately six months prior to the anticipated locking of the database. When an IRIS participant is found to have a matching record in the NDI, the record will be forwarded to the research team at the site which was managing the participant. That team will then perform a "follow-back" investigation by contacting the decedent's next of kin, physician, or hospital to confirm vital status and, if possible, the cause of death. All information on death or cause of death will be entered into the usual IRIS adjudication process. If the death is adjudicated or the cause of death is adjudicated as an MI or a stroke, the event will be included in the analyses for those outcomes. Any death identified from the NDI search on patients who were lost to follow-up that occurs after a participant's exit date, will be used as evidence of event free survival for all-cause mortality analysis only through the participant's exit date.

For complete protocol definitions of the primary and secondary outcomes see Appendix 1.

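### All-cause mortality: National Death Index deaths after last contact count, but lost participants searched without a match stay censored at last contact, which overstates mortality

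*SAP*

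**What the plan says.** All the rules are in the SAP, Study Outcomes.

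- Censoring: "Time to censoring will be defined as time in days from date of randomization until the date of last contact". Contact is narrow: "Contact will be defined as direct contact with the patient or a pre-defined surrogate".
- Databases as evidence of being event-free: "Database review will not be considered sufficient contact to determine event free time except in certain circumstances for all-cause mortality only".
- Databases as a source of events, in the next sentence but one on the same page of rules: "Events detected through database searches will be counted if adjudicated as an event". Nothing requires the event to precede last contact.
- Time limit on events: when the exit interview is missed or late, "outcome and safety events will not be counted if they occur more than 21 days after the scheduled date of an exit interview".
- Who is searched: the NDI is approached, subject to review-board approval, "for information on patients who have been lost to follow-up".
- What a match does: "If the death is adjudicated or the cause of death is adjudicated as an MI or a stroke, the event will be included". A matched death can therefore enter mortality, stroke or MI.
- The mortality exception: a death that the NDI places after the participant's exit date "will be used as evidence of event free survival for all-cause mortality analysis only", up to that exit date. No rule gives time to a participant who was searched and not matched.

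**The concern.** Take three lost participants with the same last contact. One dies before the exit date: the NDI finds the death, and the participant stays at risk until then and counts as an event. One dies after the exit date: the participant is credited as alive to exit. One has no match and, if the search is good, is probably alive: the participant leaves the risk set at last contact. How long each stays at risk is decided by what happens later. Kaplan-Meier, log-rank and Cox methods all assume that this does not happen. The exception for late deaths does not repair it, because it too depends on a later death.

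The deaths are kept and the matching survival time is dropped, so estimated mortality is too high in any arm with loss. All-cause mortality is where this matters most. It is a secondary efficacy outcome, and Analysis of Adverse Events and Appendix 1 also treat it as a safety measure.

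**Working it through.** The SAP states no loss rate and no mortality rate, so it has no figure of its own to reproduce here. Sizes are computed under stated assumptions.

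**Inputs from the SAP.** Average follow-up of about four years and about 4000 participants (Study Design). Four-year placebo primary risk of 27% (Primary Objective). 908 primary events (Monitoring for Efficacy). Five-year figures of 18% stroke, 9% MI and 6% dying of either (Background).

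**Assumed.** Death hazard d = 0.025 per year. Constant loss hazard λ, unrelated to risk. Complete search unless stated. Follow-up fixed at E = 4 years.

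**Mortality rate**

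- Deaths per person: D = 1 − exp(−dE) = 1 − exp(−0.1) = 0.0952.
- True person-time: T = D/d = 3.8065 years.
- Person-time dropped, for those lost and alive at exit: M = exp(−dE) × [E − (1 − exp(−λE))/λ].
- Proportion lost: λ/(λ+d) × [1 − exp(−(λ+d)E)].
- Overstatement of the rate: T/(T − M).

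| λ | Lost | M (years) | T/(T − M) |
|---|---|---|---|
| 0.02 | 7.3% | 0.1410 | 1.038 |
| 0.03 | 10.8% | 0.2087 | 1.058 |
| 0.04 | 14.1% | 0.2747 | 1.078 |

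The exception for deaths after exit barely helps. If the NDI ran one year past exit, it would restore 1 − exp(−0.025) = 2.5% of M, and 1.038 would become 3.8065/(3.8065 − 0.1375) = 1.037.

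**Kaplan-Meier.** Under the SAP rule the apparent hazard at time t is d / [exp(−λt) + (1 − exp(−λt))(1 − exp(−d(E − t)))]. Integrated to four years with λ = 0.02, mortality is 9.87% against a true 9.52%, or 3.8% too high.

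**Mortality ratio with no true effect**

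- Equal loss: the two inflations cancel, giving a ratio of 1.00.
- 7.3% vs 10.8% lost: 1.058/1.038 = 1.019.
- 7.3% vs 14.1% lost: 1.078/1.038 = 1.038.
- 5% vs 15% lost (λ = 0.0135 and 0.043): 1.0838/1.0259 = 1.056. A simulation with loss times spread uniformly, run at the primary outcome's hazard, gave 1.045 for the same gap.

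For scale, 4000 × 0.0952 = 381 deaths, so the standard error of the log hazard ratio is about 2/√381 = 0.102. The three shifts are about 0.2, 0.4 and 0.5 standard errors.

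**Primary outcome.** The NDI finds deaths only. From Background, the fatal share is about f = 6/(18 + 9) = 0.22. With h = −ln(0.73)/4 = 0.0787 in place of d, the relative excess is f × M/(time counted).

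- 5% lost: 0.222 × 0.0858/3.338 = 0.0057.
- 15% lost: 0.222 × 0.2621/3.146 = 0.0185.
- Ratio for 5% vs 15%: 1.0185/1.0057 = 1.013. For 5% vs 10% it is 1.006, and for 8% vs 12% it is 1.005.
- Equal loss of 10%: an excess of 0.0119 gives four-year risk 1 − 0.73^1.0119 = 27.3% against 27.0%.

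With 908 events the standard error is 2/√908 = 0.066, so the largest of these shifts is about 0.2 standard errors.

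**Alternative rules for mortality, by simulation (exits spread over 3 to 5 years)**

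- Crediting unmatched participants to exit: no bias with a complete search; −0.4% at 7.3% loss if 90% of deaths are found.
- If risk doubles after loss (assumed), with 10% lost and a complete search: the SAP rule is about 5% too high, stopping events and time at last contact is about 5% too low, and crediting is unbiased.
- Same case with 80% of deaths found: about +3%, −5% and −2% respectively.

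**The case against.** The strongest reply is that the treatment comparison is hardly touched. With equal loss and equal event-finding the hazard ratio is unbiased, and even the unequal-loss shifts are well under one standard error. That stands, and it is why the point is moderate. It does not rescue the absolute mortality rates or curves, which are too high whenever there is loss.

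Four stronger readings are tempting, and the document does not support them.

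- *The SAP expects unequal loss.* Study Design warns that early events may alter compliance with study drug by arm. That is not loss to follow-up, and the same section says participants with a stroke or MI go on being followed. Unequal loss is possible but is not stated.
- *The primary result is materially biased.* The one database described yields deaths only. The SAP does speak of database searches in general. If another source found every later stroke and MI, simulation puts four-year placebo risk at 28.1% with 10% loss in both arms, and the null hazard ratio at 1.045 with 5% vs 15% loss. Nothing in the SAP describes such a source.
- *Late exit interviews generally add time in which no event can count.* The stated maximum of 1847 days (5 × 365.25 + 21) already aligns the two for five-year exits. A gap remains only for those exiting earlier, in the March to July 2015 window, and its size was not estimated.
- *Stopping events and time together is unbiased in every case.* It is unbiased only when loss is unrelated to risk. Crediting unmatched participants is unbiased only when the search is complete.

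Removing adjudicated fatal strokes and MIs from the main intention-to-treat analysis would also be a trade-off, not a plain correction.

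**Conclusion.** The point holds for all-cause mortality. The SAP's rules make time at risk depend on the later outcome, and mortality is overstated by about 4% in relative terms at an assumed 7% loss with a complete NDI search. The mortality hazard ratio is biased, by roughly 2% to 5% over the loss gaps tried, against the arm with more loss, and only if loss or event-finding differs by arm. For the primary outcome the ratio moves by about 1% at most, at assumed loss up to 5% vs 15%. All loss rates, the 2.5% yearly mortality and the completeness of the search are assumptions, because the SAP gives none of them. Severity is moderate.

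**What to change.** 1. **All-cause mortality.** State that a lost participant submitted to the NDI and not matched counts as alive to the earlier of the exit date and the end of NDI coverage. Keep censoring at last contact for anyone not submitted, for example where review-board approval is lacking. The price is slight understatement if the NDI misses deaths.
2. **Stroke, MI and the other non-mortality outcomes.** Keep the main analysis as written. Add a named sensitivity analysis in which events and time both stop at last contact. Do not credit unmatched participants with event-free time here: the NDI says nothing about non-fatal events. In simulation of the primary outcome with 10% loss and 30% of later events found, such credit lowered the four-year risks from 27.0% and 22.0% to 25.9% and 21.3%.
3. **Exit.** For participants exiting before five years, cap censoring time at scheduled exit plus 21 days, to match the event cut-off.

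The cost is a few sentences in the SAP, a few lines in the derivation of event and censoring dates, and one further sensitivity run. It needs the list of participants submitted to the NDI and the coverage date of each search. It should be settled before unblinding.
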